# 5.8.4.3 Proportion of Participants with Hemoglobin A1c ≥ 5.7% after 13 Week of Treatment

Post-baseline Last observation carried forward (LOCF) approach will be used to impute missing value at Week 13. Only assessments, for subjects who are on treatment for more than 28 days, collected on or before treatment discontinuation + 3 days will be used for LOCF. Number and percent of participants with hemoglobin A1c  $\geq$  5.7 % will be summarize at baseline and week 13 by treatment group.

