#### **Approach to Maximizing Gut Hormone Secretion from EECs**

[REDACTED] Because GPR40 and GPR119 use distinct second messengers for signaling, co-agonism on cells expressing both receptors would be predicted to result in enhanced hormone secretion vs single agent therapy (24,25).

[REDACTED]

GPR40 is activated by medium to long-chain fatty acids (LCFA) (25). Stimulation by LCFAs or synthetic *partial* GPR40 agonists results in enhanced glucose-dependent insulin secretion (GDIS) presumably due to GPR40 activation directly on pancreatic  $\beta$ -cells, though such partial agonists do not enhance the secretion of gut satiety peptides. Synthetic full agonists of GPR40 do stimulate robust secretion of gut peptides in addition to GDIS (25). GPR119 is activated by medium chain fatty acids. In participants with T2DM, administration of agonists of GPR40 or GPR119, results in improved glucose control in humans, although the glucose lowering effects observed with GPR119 agonists are very modest (5,6,26). To date there are no reports of co-administration of a GPR40 and GPR119 agonist in humans and single agent therapy to date has not resulted in weight loss.

K-757 is a novel, highly selective, gut restricted full activator of GPR40.

[REDACTED]

[REDACTED] K-833 is a novel oral gut restricted small molecule agonist of GPR119 [REDACTED]

[REDACTED] mportantly, and consistent with preclinical data, fasiglifam, a partial agonist, does not result in stimulation of gut peptide secretion and did not induce weight loss in human studies.

[figure not shown]
SCO-267, a GPR40 full agonist, is currently in Phase 1 development and activates both pancreatic and gut GPR40, stimulates gut hormones secretion, and improves oral glucose tolerance. Some generally mild dose-dependent GI AEs of nausea were reported which are likely related to secretion of gut hormones. A few AEs of increased AST/ALT were reported with this molecule in Phase 1 studies and were rated as “mild” in intensity. No signs or symptoms of liver toxicity were reported.

Potential liabilities of certain GPR40 full agonists observed in preclinical species include depletion of pancreatic  $\beta$  cell insulin content, which was reported in one strain of rats and resulted in hyperglycemia.

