### Glycemia related:

1. Has a HbA1c  $\geq 6.5\%$  (48 mmol/mol) as measured by the central laboratory at screening.
2. Has a history of clinically significant endocrine disease including T2DM.

**Note:** A history of hypothyroidism does not require exclusion if the subject has been on a stable dose of thyroid hormone replacement (thyroxine) for at least 3 months prior to screening and the screening TSH is within the central laboratory normal range.

3. Has a history of type 1 or type 2 diabetes mellitus.
4. Had treatment with any glucose-lowering agent(s) within 90 days before screening.

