#### **5.11.2** Clinical laboratory Assessments

The clinical laboratory parameters presented in Table 3 will be assessed at the specific times as outlined in the SOA (Error! Reference source not found.).

Observed values and change from baseline to each visit and time point during on-treatment period (from first dose date up to 2 weeks after the last dose of the study medication) and follow up visit in the clinical laboratory parameters for hematology and clinical chemistry will be summarized by treatment group, using descriptive statistics.

In addition, hematology and clinical chemistry parameters during on-treatment period that meet the Sponsor's pre-defined limits of change as presented in Table 4 will be summarized by treatment group, using frequency and percentage.

Clinical laboratory test parameters for hematology, clinical chemistry and urinalysis along with the associated reference ranges will be listed for individual subjects; abnormal values will be flagged as high or low in the listings. Individual measurements of laboratory tests from hematology, chemistry, and urinalysis that meet the abnormal criteria will be categorized to and listed by not clinical significant and clinical significant. Other clinical laboratory tests, such as,

virus serology, COVID-19 testing, drug screen, pregnancy, and follicle stimulating hormone (FSH) will be presented listings only.

Laboratory data will be summarized or listed in International System of Units (SI).

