# APPANDIX 2 Clinical Laboratory Assessments

Table 3: Protocol-Required Laboratory Assessments

Hematology	
White blood cell (WBC) count a	Hemoglobin
Red blood cell (RBC) count b	Hematocrit
Platelet count	HbA1c
Clinical Chemistry	
Alanine aminotransferase (ALT)	Phosphorus
Albumin	Potassium
Alkaline phosphatase (ALP)	Sodium
Aspartate aminotransferase (AST)	Total bilirubin
Bicarbonate	Direct bilirubin
Chloride	Total Protein
Cholesterol (full lipid panel on Day 1 and EoT only)	Triglycerides
Creatinine	Urea
Calcium	Gamma-glutamyl transferase (GGT) c
Glucose	Magnesium
TSH (Screening)	Multiple biochemical analysis (MBA) c
	Amylase
	Lipase
Urinalysis	
Dipstick:	Microscopic:
Nitrite	WBC
Protein	RBC
Glucose	Epithelial cells
рН	Casts (specify)
Specific gravity	
Ketones	
Bilirubin	
Urobilinogen	
Leucocyte Esterase	

DI I	
Rlood	
Diood	

<sup>a Differential white blood cell count will include percentages for neutrophils, lymphocytes, monocytes, eosinophils, and basophils and absolute counts for neutrophils, lymphocytes, monocytes, eosinophils, and basophils.

Table 4: Pre-Defined Limits of Change for Laboratory Parameters and Electrocardiogram

Hematology	
Hemoglobin (g/dL)	1. Decrease ≥ 1.5 g/dL
	2. Increase $> 2.0 \text{ g/dL}$
	3. Increase > 2.0 g/dL and value > ULN
	Both criteria 2 and 3 will be flagged.
WBC count (103/microL)	1. Decrease ≥50% and value < LLN
	2. Increase ≥20% and value > ULN
Neutrophil count(10  /microL)	1. Decrease ≥20% and value < LLN
-	2. Increase ≥20% and value > ULN
Lymphocyte count (10  /microL)	1. Decrease ≥20% and value < LLN
	2. Increase ≥20% and value > ULN
Platelet count (10  /microL)	1. Decrease ≥25% and value < LLN
,	2. Increase ≥100% and value > ULN
Clinical Chemistry	 
BUN mg/dL	Increase ≥ 50% and value > ULN
Total bilirubin mg/dL	Value > 2x ULN
AST (IU/L)	Value ≥ 3x ULN
	Value > 5x ULN
	Value > 10 x ULN
	Value > 20x ULN
ALT (IU/L)	Value ≥ 3x ULN
	Value > 5x ULN
	Value > 10 x ULN
	Value > 20x ULN
AST or ALT (IU/L)	Value ≥ 3x ULN
	Value > 5x ULN
	Value > 10 x ULN
	Value > 20x ULN
AST or ALT (IU/L) + Total bilirubin (mg/dL)	AST or ALT ≥3x ULN with concurrent bilirubin > 2x ULN
Alkaline phosphatase (IU/L)	Value > 1.5x ULN
Sodium (mmol/L)	1. Decrease ≥ 10 and value <lln< td=""></lln<>
	2. Increase ≥ 10 and value >ULN
	3. Value > 155
Potassium (mmol/L)	1. Decrease ≥ 1 and value <lln< td=""></lln<>

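### SAP 5.8.4.3 reports only the net share with HbA1c at or above 5.7%, and Table 4 has no glucose or HbA1c row, so no planned laboratory table counts by arm the participants whose glycemia worsens

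*SAP*

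**What the plan says.** **HbA1c.** SAP 5.8.4.3 plans one display, the number and percent of participants at or above 5.7%, which "will be summarize at baseline and week 13 by treatment group". A missing Week 13 value is filled by carrying the last post-baseline value forward, restricted to values "for subjects who are on treatment for more than 28 days, collected on or before treatment discontinuation + 3 days will be used for LOCF". The section has no baseline-by-Week-13 cross-tabulation, no count of new cases and no category at 6.5% or above.

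**Categorical laboratory counts.** SAP 5.11.2 counts values that meet the limits in Table 4, "Pre-Defined Limits of Change for Laboratory Parameters and Electrocardiogram". That table has rows for hemoglobin, white cells, transaminases, electrolytes and others, but none for glucose or HbA1c.

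**Other laboratory output.** SAP Table 3 lists HbA1c under hematology and glucose under clinical chemistry. Under SAP 5.11.2, observed values and changes from baseline "in the clinical laboratory parameters for hematology and clinical chemistry will be summarized by treatment group, using descriptive statistics". SAP 5.1.1 defines those statistics as n, mean, SD, minimum, quartiles and maximum. Individual values are listed with high or low flags.

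**Why glycemia is of interest.** Protocol 5.1 says: "K-757 is a novel, highly selective, gut restricted full activator of GPR40". Among possible liabilities of some GPR40 full agonists in animals it lists loss of beta-cell insulin content, "which was reported in one strain of rats and resulted in hyperglycemia". Protocol Table 2 schedules HbA1c at Visits 1, 2 and 12, and fasting chemistry at Visits 2, 6, 9, 12 and 13.

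**The concern.** A share at two time points shows only net movement. In a weight-loss trial some participants are likely to fall below 5.7%, more so in an arm that works, and each one cancels a participant who rises above it. Movement inside the upper group is not seen at all. Exclusion criterion 1 allows entry with any HbA1c below 6.5%, so a participant can start at 5.8%, finish at 6.6% (above the trial's own entry ceiling) and be counted identically at both times.

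The mean change has the same weakness, because many small falls can outweigh a few larger rises. A reader comparing arms on the tabulated share could take a flat or falling figure to mean that nobody worsened. The protocol states that the trial is to inform whether the regimens merit further evaluation, so a count by arm on a named class liability is worth having.

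**Working it through.** **The plan's own figure.** The documents give no figure for HbA1c or glucose. The only design figure is power above 95% for body weight. With 50 per arm less 20% dropout, n = 40: power = Φ(4 / (4 × √(2/40)) − 1.96) = Φ(4.472 − 1.960) = 0.994, so it reproduces. It does not bear on this point; only n = 40 is used below.

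**1. Netting.** Among participants with both values,

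Week 13 count = baseline count − improvers + new cases.

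The share is unchanged whenever improvers equal new cases. Take n = 40. The baseline share and the 30% improvement rate are assumptions, with counts rounded to whole participants:

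| Baseline share ≥5.7% | High at baseline | Improve (30%) | New cases that leave the share unchanged |
|---|---|---|---|
| 20% | 8 | 2 | 2 of 32 (6.2%) |
| 30% | 12 | 4 | 4 of 28 (14.3%) |
| 40% | 16 | 5 | 5 of 24 (20.8%) |
| 50% | 20 | 6 | 6 of 20 (30.0%) |

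With improvement varied from 15% to 50%, the range runs from 1 of 32 (3.1%) to 10 of 20 (50%).

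**2. Illustration by simulation.** All inputs are assumed: baseline mean 5.5%, SD 0.35, truncated below 6.5%; a harmed fraction rises by 0.6 points; the rest fall by 0.12; noise SD 0.12.

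| Harmed fraction | Share ≥5.7%, baseline to Week 13 | Newly ≥5.7% among those below |
|---|---|---|
| 5% | 28% to about 22% | about 5.5% |
| 10% | 28.1% to 25.8% | 9.4% |
| 15% | 28% to 29% | about 13% |

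At 10% harmed, 71.9% start below 5.7%. New crossings are 0.719 × 9.4% = 6.8 percentage points of the arm. The net change is 25.8 − 28.1 = −2.3 points, so about 6.8 + 2.3 = 9.1 points moved down. The mean change is −0.05, and 1.4% of the arm end at 6.5% or above.

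**3. What the already planned statistics would show in the same model.** At 10% harmed the third quartile of change is about 0.00, so the quartiles show no rise. The SD of change is about 0.25, against 0.12 in an arm with no effect and the same noise. The maximum change in an arm of 40 is typically about +0.7, against about +0.25, and it exceeds +0.4 in 98% of such arms against 2% with no effect. At 5% harmed it exceeds +0.4 in 86%.

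**4. What noise does to the proposed count.** With no true change, about 7% of those starting below 5.7% still cross upward. With about 29 of 40 starting below (0.719 × 40), that is 29 × 0.07 = 2.0 participants, against 29 × 0.094 = 2.7 at 10% harmed.

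**The case against.** A reader might infer that the hyperglycemia risk is hidden, or that the trial would present it as a benefit. The documents do not support either reading.

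- SAP 5.11.2, with Table 3 and SAP 5.1.1, already reports SD, quartiles and extremes of HbA1c and glucose change by arm, with flagged listings and abnormal values listed by clinical significance. In the illustration, the SD and maximum expose the harmed subgroup.
- Clinically significant laboratory changes may be recorded as adverse events (Protocol 15.2.1.1), and these are tabulated by arm.
- SAP 5.8.4.3 is a descriptive count with no test and no claim of benefit, and HbA1c is not a listed endpoint. At 15% harmed the share rises rather than falls.
- The liability is preclinical, seen in one rat strain with some agonists, and K-757 is described as gut restricted. Nearby text is redacted, so the sponsor's full assessment cannot be read.
- The table shells are in a separate document and may already contain more.

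All of this stands and limits the point. It does not close the gap. A maximum describes one participant and does not say how many worsened. Listings are not summarized by arm. An adverse event entry depends on the investigator's judgement. The one HbA1c table with a threshold still nets opposite movements.

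**Conclusion.** The gap is real but modest. As written, the SAP has no laboratory table that counts, by arm, participants whose HbA1c or fasting glucose worsens past a threshold, and its one HbA1c threshold table cannot show offsetting movement or movement above 5.7%. The marginal share could therefore mislead a reader who relies on it. The information is not absent from the output; what is missing is a count.

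The netting identity needs no assumption. Its size does: 1 to 10 offset cases per 40 rests on assumed baseline shares of 20% to 50% and improvement of 15% to 50%, and every simulation input is assumed. The proposed count is also a weak signal on its own, at 9.4% against about 7% from noise alone. It is useful as description beside placebo and is not a test. This is a low-cost improvement that should be made; it does not threaten the trial's conclusions on weight.

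**What to change.** 1. In SAP 5.8.4.3, add to or replace the two shares with a baseline-by-Week-13 HbA1c shift table for each arm, placebo included, with categories below 5.7%, 5.7% to 6.4%, and 6.5% or above. Both cut-points are already in the documents (SAP 5.8.4.3 and exclusion criterion 1).
2. Beneath it, report the number newly at or above 5.7% among those below at baseline, and the number newly at or above 6.5%. State that these are read against placebo, because noise alone produces crossings at 5.7%.
3. Add a treatment-emergent fasting glucose row to SAP Table 4, with reporting cut-points chosen by the sponsor. This is a display rule only and implies no change to clinical management.

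The cost is SAP wording and one or two descriptive tables. No visit, sample or test is added, and the SAP already uses a shift format for physical examination (SAP 5.11.5). The downside is small, noisy counts at about 50 per arm.

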#### 5.9 Pharmacokinetic Analysis

PK analyses for K-757 and K-833 will be performed based on the PK Analysis Set.

Plasma concentration of K-757 or K-833 at the timepoints specified in the SOA (Table 2) will be descriptively summarize by treatment arm with n, mean, SD, median, minimum, maximum, geometric mean and geometric CV%, as appropriate.

For the purpose of descriptive summaries, plasma concentrations of K-757 or K-833 below the lower limit of quantification (BLQ) will be set to zero except for calculating geometric means and geometric CV%. For the geometric means and geometric CV%, the BLQ value is set to LLOQ/2.

The PK concentrations will be displayed with the same precision as concentration data received, but no more than 3 decimal places. In descriptive statistics, calculations derived from PK concentrations will follow the same precision. The CV% will be displayed with one decimal place.

Raw PK concentrations in ng/mL will be converted to nM for each study drug. The molecular weight for K-757 is 541.71 and the molecular weight for K-833 is 640.15. Specifically, the following formula will be used to convert from ng/mL to nM: (concentration in ng/mL /molecular weight)  $\times$  1000 = concentration in nM.

A by-subject listing will be provided.

#### 5.10 Pharmacodynamic Analysis and DNA Sample

PD parameters including gut hormone levels (eg. GLP-1, PYY) assessed in samples collected at the timepoints specified in the SOA (Table 2) may be summarized.

Results of any analyses performed on the optional genetic blood sample (Table 2) may be summarized.

#### 5.11 Safety Analyses

The safety measurements include AEs, clinical laboratory assessments, vital signs, 12-lead ECG and physical examination. All summaries will be performed and reported by treatment group using the Safety Analysis Set.

No formal statistical tests or inference will be performed for safety analyses.

#### 5.11.1 Adverse Events

An AE is any untoward medical occurrence in a patient or clinical investigation subject administered a pharmaceutical product and which does not necessarily have to have a causal relationship with this treatment. All AEs will be recorded starting from the signing of informed consent form throughout the end of the follow-up or early study termination.

A TEAE is defined as an AE that starts or worsens after the time of randomization up to 2 weeks after the last dose of the study medication.

A SAE is defined as any untoward medical occurrence that:

- Results in death
- Is immediately life threatening
- Requires in-patient hospitalization or prolongation of existing hospitalization
- Results in persistent or significant disability or incapacity

- Results in a congenital abnormality or birth defect
- Is an important medical event that may jeopardize the patient or may require medical intervention to prevent one of the outcomes listed above.

All AEs will be coded and classified using the version of the Medical Dictionary of Regulatory Activities (MedDRA) in affect at the start of the study. The severity/intensity of AE is assessed by the Investigator as mild, moderate or severe. The relationship to study drug is judged by the Investigator as related or unrelated.

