### **8.3. Subject Withdrawal Criteria**

#### **8.3.1. Procedures for Discontinuation or Withdrawal of a Subject**

##### **8.3.1.1. Discontinuation of Trial Treatment**

Discontinuation of trial product can be decided by either the investigator or the subject. A participant may discontinue his or her participation without giving a reason at any time during the trial.

Participants who discontinue trial product should continue with the scheduled visits and assessments to ensure continued counselling and data collection.

If the subject does not wish to attend the scheduled clinic visits, efforts should be made to have the visits converted to phone contacts. However, all efforts should be made to have the subject attend at least the 'end of treatment' clinic visit containing the final data collection of primary and confirmatory secondary efficacy endpoints, and the 'end of trial' visit.

The 'end of trial' visit is scheduled approximately 2 weeks after the final data collection, to ensure the safety of the subject. If the subject has discontinued trial product >2 weeks prior to the 'end of treatment' visit, and the requirements for the follow-up period prior to the 'end of trial' visit is fulfilled, then the 'end of trial' visit can be performed in combination with 'end of treatment' visit.

If the subject refuses to attend the 'end of treatment' and/or 'end of trial' visit, information about the attempts to follow up with the subject must be documented in the subject's medical record.

The subject must be discontinued from trial product if any of the following applies:

1. Safety concern as judged by the investigator
2. Pregnancy
3. Intention of becoming pregnant
4. Liver function test (LFT) abnormalities meeting specified discontinuation criteria (refer to [Appendix A](#) for discontinuation criteria and instruction on management of LFT abnormalities)
5. Confirmed pancreatitis (see below)

If acute pancreatitis is suspected based on clinical signs and symptoms, blinded study medication should be interrupted immediately, and appropriate diagnostic assessments should be performed.

- A diagnosis of acute pancreatitis requires at least 2 of the following 3 findings :
  - abdominal pain consistent with acute pancreatitis (persistent, severe epigastric pain, frequently radiating to the back); abdominal pain is often associated with nausea and vomiting.
  - serum lipase and/or amylase activity  $\geq 3X$  the laboratory ULN

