### **15.2.2. Time Period and Frequency for Collecting AE and SAE Information**

All AEs and SAEs will be collected from time of consent through the Poststudy/End of Trial visit.

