### **15.2.4. Recording of AEs and SAEs**

All AEs that occur after any patient/subject has been consented, before treatment, during treatment, during all visits, and within 14 days following the cessation of treatment, whether or not they are related to the study drug, must be recorded on the eCRFs provided by Kallyope, Inc.

Each event should be recorded to represent a single diagnosis. Accompanying signs (including abnormal laboratory values or ECG findings) or symptoms should NOT be recorded as additional AEs. If a diagnosis is unknown, sign(s) or symptom(s) should be recorded appropriately as an AE(s) and updated once the information becomes available.

The following information will be documented for each event:

- Event term
- Start and end date and time
- Pattern of AE (frequency)
- Severity/intensity
- Causality Assessment (Investigator's opinion of the causal relationship between the event and administration of study drug[s])
- Action taken with trial drug
- Outcome of event
- Seriousness

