### **16.7.1. Treatment-emergent Adverse Events (TEAE)**

Safety analyses will be based on the Safety Analysis Set. No formal statistical tests or inference will be performed for safety analyses.

Adverse events will be coded using the version of the Medical Dictionary for Regulatory Activities (MedDRA) in effect at the start of the study. AEs will be summarized as TEAEs (defined as events that are newly reported after randomization or reported to worsen in severity from baseline). The incidence of participants with at least 1 TEAE and the incidence of TEAEs by preferred term and system organ class will be presented by treatment group. The frequency and percentage of TEAEs will be presented. The incidence of participants with at least 1 TEAE assessed as related to the study drug will be summarized by treatment group. All SAEs will be listed by patient. If a sufficient number of SAEs are reported, summaries will be included. Discontinuations to study and study drug due to TEAEs will be summarized by treatment group. All adverse events will be listed by patient.

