#### 8 Changes from Pre-specified Analyses in the Protocol

There were no changes in the analyses or definitions planned in the CSP.

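### The SAP ends the TEAE window 2 weeks after the last dose, the protocol gives it no end, and SAP Section 8 declares no change; late events in early stoppers drop out of the TEAE, SAE and fatal-event tables

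*SAP*

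**What the plan says.** **Counting.** Protocol Section 16.7.1, like the synopsis, has TEAEs "defined as events that are newly reported after randomization or reported to worsen in severity from baseline". No upper limit is given. SAP Section 5.11.1 counts an event that "starts or worsens after the time of randomization up to 2 weeks after the last dose of the study medication". SAP Section 5.11.1.2 uses the same cut-off, or end of study if earlier, as its on-treatment period for safety analyses. SAP Section 8 then says: "There were no changes in the analyses or definitions planned in the CSP".

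**Recording.** Protocol Section 15.2.2: "All AEs and SAEs will be collected from time of consent through the Poststudy/End of Trial visit". SAP Section 5.11.1 agrees: "All AEs will be recorded starting from the signing of informed consent form throughout the end of the follow-up or early study termination". Protocol Section 15.2.4 lists the periods differently: after consent, before and during treatment, "during all visits, and within 14 days following the cessation of treatment".

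**Follow-up after stopping drug.** Protocol Section 8.3.1.1: "Participants who discontinue trial product should continue with the scheduled visits and assessments". The same section allows the End of Trial visit to be combined with the end-of-treatment visit when drug was stopped more than 2 weeks before the latter.

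**What is reported.** The proportion of participants with at least one TEAE is a secondary endpoint in both documents (SAP Section 2.2.2). SAP Section 5.11.1.1 tabulates treatment-emergent SAEs and TEAEs with fatal outcome, and lists all AEs and all SAEs by subject. The protocol synopsis says all SAEs will be both summarized and listed. Protocol Section 16.7.1 lists all SAEs and summarizes them only if there are enough.

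**The concern.** A secondary endpoint has two definitions and the SAP says it has one. The difference falls almost entirely on people who stop drug early and stay in the trial. Take a participant whose last dose is on Day 22 and who has an SAE on Day 60. The event is treatment-emergent under protocol Section 16.7.1. Under the SAP it is not, because the window closed on Day 36, so it enters neither the TEAE tables nor the treatment-emergent SAE table. If it were fatal, it would also be missing from the fatal-outcome count. It would appear only in the by-subject listings, although the synopsis promises a summary of all SAEs.

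Two things are at stake. One is traceability: a reader of the study report could not tell from SAP Section 8 that the definition was narrowed. The other is completeness: no planned table would show serious or fatal events by arm over the whole period in which participants are followed.

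**Working it through.** **Inputs.** Last scheduled dose Day 91, end-of-treatment visit Day 92, post-study visit Day 105 ± 3 days (protocol Section 7.1 and Table 2); 50 participants per arm (protocol Section 7.2); SAP window closing at last dose + 14 days; End of Trial visit for an early stopper either combined with Day 92 or held at Day 105 (protocol Section 8.3.1.1 and Table 2).

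**Check of the plan's own figure.** The protocol puts follow-up at about 14 days after the last dose. For a completer, 105 − 91 = 14 days, so the figure is reproduced. With the visit window it is 102 − 91 = 11 to 108 − 91 = 17 days. A completer seen on Days 106 to 108 is therefore 15 to 17 days past the last dose, a small overrun.

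**Early stoppers.** For a last dose on Day L, the SAP window closes on Day L + 14. Days outside it = final visit day − (L + 14).

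| Last dose | SAP window closes | Outside it, final visit Day 92 | Outside it, final visit Day 105 |
|---|---|---|---|
| Day 22 | 22 + 14 = Day 36 | 92 − 36 = 56; 56/92 = 61% | 105 − 36 = 69; 69/105 = 66% |
| Day 57 | 57 + 14 = Day 71 | 92 − 71 = 21; 21/92 = 23% | 105 − 71 = 34; 34/105 = 32% |
| Day 91 | 91 + 14 = Day 105 | 0 | 0 |

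The days in Day 22 and Day 57 are examples, chosen to show an early and a mid-trial stop.

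**When the endpoint moves.** The endpoint counts participants, not events. A participant is classified differently only if the first TEAE starts after Day L + 14 and before the final visit. Anyone with a TEAE on drug, or in the 14 days after it, is counted under both rules. Each participant who is classified differently moves the arm's proportion by 1/50 = 2 percentage points. The documents give no basis for the number of such participants.

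**Other tables.** Preferred-term, severity, SAE and fatal-event tables can change for any late event of the relevant kind, whether or not the participant had an earlier TEAE. They are more exposed than the binary endpoint.

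**Not affected.** The other safety endpoint, stopping study medication because of an AE, is the same under both windows.

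**The case against.** The SAP's window is a legitimate choice. Protocol Section 11.2 puts 14 days at more than 5 times the estimated half-life of both drugs, so leaving later off-drug events out of a treatment-emergent table is defensible. This stands: making the wider window the main table would be a preference, not a correction.

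Late events are not hidden. All AEs and all SAEs are listed by subject, there is no formal safety testing, and protocol Section 16.7.1 itself makes SAE summaries conditional on number. This stands in part: listings preserve the events but give no comparison by arm, and the synopsis is unconditional.

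A reader might infer that sites will leave late events unrecorded because of the 14-day phrase in protocol Section 15.2.4. The documents do not support that. The periods in that sentence are cumulative and include all visits, early stoppers keep attending visits, and protocol Section 15.2.2 and SAP Section 5.11.1 both carry recording to the end of follow-up. The sentence is loose, not a clear conflict. If it were applied as a strict limit, later events would not be in the database and the two TEAE definitions would give nearly the same count, so both harms could not occur in full.

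A reader might also infer that the active arms' TEAE incidence is understated because GI intolerance would cause more early stopping there. For the named endpoint the mechanism largely cancels itself: someone who stops for a GI event has normally already had a TEAE and is counted. The protocol also rates the risk of a high discontinuation rate as low (Section 5.4). Differential bias is possible, mainly in the other tables, but not shown.

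**Conclusion.** The concern holds as an undeclared change of definition. Protocol Section 16.7.1 and the synopsis have no end to the TEAE window, SAP Section 5.11.1 ends it 2 weeks after the last dose, and SAP Section 8 is wrong to say that nothing changed. It is wrong whichever window the sponsor prefers.

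The endpoint can differ between the two documents, by 2 percentage points for each participant (of 50 in an arm) whose first TEAE is late. A total cannot be derived. It would be tempting to use the 20% drop-out from the sample-size section: 10 of 50 per arm, and if 30% of them had a late first event, 3 of 50, or 6 points. That would assume that every drop-out stops drug yet stays in follow-up, and the 30% has no source. Those who leave the trial contribute no later events under either rule.

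What can be stated is the share of follow-up outside the SAP window for participants who stop early and stay: 61% to 66% for a last dose on Day 22 and 23% to 32% for Day 57, depending on when the final visit takes place. The primary efficacy analysis is not touched. The correction should be made because it is cheap and because the plan lacks a table of late serious and fatal events.

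**What to change.** 1. State one TEAE window in both documents. The 2-week window is acceptable if declared; SAP Section 8 must then list it as a change from the definition in protocol Section 16.7.1 and the synopsis.
2. Keep the 2-week tables in SAP Section 5.11.1.1 and add, beside them, a summary by arm of all AEs, SAEs and deaths from randomization through the End of Trial visit, on or off drug. This also meets the synopsis commitment to summarize all SAEs.
3. As a clarification of wording, align protocol Section 15.2.4 with Section 15.2.2, so that recording through the End of Trial visit is explicit for every participant.

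The cost is a sentence in the protocol, a few lines in the SAP and one repeat set of tables. No visits or data items are added, because early stoppers are already asked to attend. The downside is that some late events unrelated to drug will enter the wider table; the 2-week table beside it lets the reader separate them.
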